**Involved-field Radiotherapy Combined With
Concurrent Intrathecal-MTX Versus Intrathecal-Ara-C
for Leptomeningeal Metastases From Solid Tumor: A
Randomized Phase II Clinical Trial**

NCT number: NCT03082144

IRB approval date: February 1, 2017

Study Protocol

Objective:

This study was designed to investigate the efficacy and safety of concurrent involved-field radiotherapy and intrathecal chemotherapy for patients with leptomeningeal metastases from solid tumors. Furthermore, another purpose of the study is to compare the two intrathecal chemotherapy drugs in the concomitant therapeutic modality.

Design:

It is a prospective, randomized controlled, parallel group, and phase II clinical trial. The study participants were newly diagnosis patients with leptomeningeal metastases from solid tumors. Patient with hematological malignancy (e.g., leukemia and lymphoma) or primary brain tumor was excluded.

In our previous study ^[1], it has been proved that concurrent radiotherapy and intrathecal methotrexate (MTX) for leptomeningeal metastases (LM) from solid tumors with adverse prognostic factors showed great effectiveness and safety. This treatment regimen improved the prognosis of LM patients from solid tumors with adverse prognostic factors for the first time. The findings suggest that the concomitant regimen could be an optimal treatment option for LM. MTX and cytarabine (ara-C) are conventional cytotoxic drugs, which are the most frequently used agents for intrathecal chemotherapy. The common regimen of intrathecal dose of MTX and ara-C was 15mg and 50mg, respectively.

This study was approved by the Ethic Committee of The First Hospital of Jilin University on February 1, 2017. All procedures were compliant with the Declaration of Helsinki. The study plan and regimen schema is provided in

Figure 1,2. The patients were randomly divided into two groups, who will accept the treatment of involved-field radiotherapy (RT) combined with concurrent intrathecal-MTX or intrathecal-ara-C, respectively. Concomitant regimen consisted of intrathecal chemotherapy (via lumbar puncture, MTX 15 mg, plus dexamethasone 5 mg, or ara-C 50mg, plus dexamethasone 5 mg, once per week, 4 weeks in total) and RT. RT consisted of fractionated, conformal radiation given at a daily dose of 2 Gy. The planning volume consisted of sites of symptomatic disease, bulky disease observed on MRI, including the whole brain and basis cranii received 40 Gy in 20 fractions and/or segment of spinal canal received 40-50 Gy(the first lumbar vertebra and the above segments were given 40 Gy in 20 fractions; the first lumbar vertebra and the inferior segments were given 40/50 Gy in 20 fractions). Patients with Karnofsky performance status score (KPS) of ≤ 40 and irradiation intolerance were required to receive induction intrathecal chemotherapy (MTX 15 mg, or ara-C 50mg, plus dexamethasone 5 mg, twice per week). Then these patients were allowed to receive concomitant therapy upon neurologic improvement and radiotherapy tolerance.

The primary endpoint was clinical response rate (CRR). The secondary endpoints were safety and overall survival (OS).

Methods:

We adopted the criteria of evaluation for clinical response established in our previous study based on improvement of neurologic symptoms/signs and changes of KPS ^[1]. The criteria have been proved associated with the prognosis of LM patients and suitable for clinical application. The clinical response was evaluated by at least two experienced neuro-oncologists. The evaluation consists of 5 layers, including complete response (CR), obvious response (OR), partial response (PR), stable disease (SD) and progressive disease (PD) (Table 1). Clinical evaluation was performed once per week from the beginning of LM-related therapy, till 2 weeks later after salvage therapy.

Clinical response was defined as continuous presence of CR, OR or PR within an interval of at least 1 week. SD and PD were defined as ineffective. Adverse events (AEs) were evaluated according to the Common Terminology Criteria for Adverse Events (CTCAE, version 3.0). Events of grade 3~5 was defined as moderate and severe adverse events. Survival time was measured from the enrollment of the study until death or the last follow-up.

[figure not shown]
Statistical Analysis Plan

SPSS 17.0 software was used for data analysis. Survival analysis was performed using the Kaplan-Meier method. Log-Rank test was used to compare the survival time of patients. Univariate and multivariate Cox regression analysis were carried out to determine the risk factors of OS. Chi square test and Fisher exact test were used to evaluate the difference of clinical response rate and OS between patients with various features. $P < 0.05$ demonstrated significant difference.

References:

[figure not shown]
Figure 1

LM: Leptomeningeal metastasis;
IC: intrathecal chemotherapy;
Ara-C: Cytarabine ;
OS: overall survival;

RT: involved-field radiotherapy;
MTX: Methotrexate ;
CRR: clinical response rate;
AD: adverse events.

Figure 2

IF-RT: involved-field radiotherapy; IC: intrathecal chemotherapy.

↓ Involved-field radiotherapy: daily: 20 × 200 cGy, total dose: 40 Gy.

↑ Intrathecal chemotherapy: Methotrexate 10 mg/ Cytarabine 50mg+dexamethasone 5 mg.

* Induction therapy were those with a Karnofsky performance status score of ≤ 40 and with no tolerance to radiotherapy.

Table 1 **Criteria of clinical response evaluation**

	Neurological symptoms and signs	KPS score
Complete response	Almost normal neurological examination. Mild cranial nerve symptoms including tinnitus or blurred vision may exist. GCS score of 15.	≥90
Obvious response	Significant neurologic improvement. No severe symptoms/signs, such as severe headache, somnolence, mental status. Dizziness, confusion, mild headache, cranial nerve paralysis, or radiculitis may exist. GCS≥12.	≥ 70, or elevation of ≥ 30 compared with the baseline level.
Partial response	Partial neurological improvement. Still with headache, or other mild/moderate symptoms/signs. GCS≥9.	50-70, or elevation of 10-20 compared with the baseline level.
Stable disease	No visible neurological improvement.	Elevation of ≤ 10 compared with the baseline level.
Progressive disease	Deteriorative neurological symptoms and signs.	Decrease of KPS compared to the baseline level.

Two conditions both of neurological symptoms/signs and KPS must be satisfied synchronously.

KPS, Karnofsky performance status score; GCS, Glasgow Coma Scale.

The clinical response was evaluated by at least two experienced neuro-oncologists. Clinical evaluation was performed twice per week from the beginning of LM-related therapy, till 2 weeks later after salvage therapy. Clinical response was defined as continuous presence of complete response (CR), obvious response (OR), partial response (PR) within an interval of at least 1 week. Stable disease (SD) and progressive disease (PD) were defined as ineffective.

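### The 50 Gy lower-spine option cannot be delivered at the stated 2 Gy per day: 20 such fractions give 40 Gy, and 50 Gy over 20 fractions needs 2.5 Gy each

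*Combined protocol and SAP*

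**What the plan says.** The radiotherapy paragraph of the Design section opens with a general rule: "RT consisted of fractionated, conformal radiation given at a daily dose of 2 Gy". It then gives total dose and fraction count by site:

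- Brain and skull base: "the whole brain and basis cranii received 40 Gy in 20 fractions".
- Upper spine: "the first lumbar vertebra and the above segments were given 40 Gy in 20 fractions".
- Lower spine: "the first lumbar vertebra and the inferior segments were given 40/50 Gy in 20 fractions".

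The Figure 2 legend describes one course only: "Involved-field radiotherapy: daily: 20 × 200 cGy, total dose: 40 Gy". The drawing itself is not available, but the legend text is.

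Intrathecal drug in the concomitant phase is given "once per week, 4 weeks in total". The Objective section says the trial is to "investigate the efficacy and safety of concurrent involved-field radiotherapy and intrathecal chemotherapy", and the Design section lists safety as a secondary endpoint.

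**The concern.** Total dose is dose per fraction times number of fractions. The protocol states all three quantities for the lower spine, and for the 50 Gy option they cannot all be true. A centre following the text must give up the 2 Gy rule, the count of 20, or the 50 Gy total.

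The choice matters clinically. A patient prescribed 50 Gy to the lower spine could receive 2.5 Gy × 20 or 2 Gy × 25. These differ in fraction size, duration and biological dose, and the patient is also receiving intrathecal chemotherapy. Because the objective covers the safety of the combined regimen itself, radiotherapy is part of what is being evaluated. If delivered fractionation is not reported, toxicity in these patients is hard to interpret or reproduce.

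**Working it through.** **Inputs** (Design section and Figure 2 legend)

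- Dose per fraction: 2 Gy. The legend's 200 cGy per fraction confirms that the daily dose is a single fraction.
- Fractions: 20 at every site where a count is given.
- Total dose: 40 Gy for brain and upper spine; 40 or 50 Gy for lower spine.

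**Step 1. Reproduce the plan's own figures.** Total = dose per fraction × fractions = 2 × 20 = 40 Gy. The legend gives 20 × 200 cGy = 4000 cGy = 40 Gy. This matches the brain, the upper spine, the 40 Gy lower-spine option and the legend.

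**Step 2. Test the 50 Gy option.**

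| Held fixed | Calculation | Result | What breaks |
|---|---|---|---|
| 50 Gy and 20 fractions | 50 / 20 | 2.5 Gy per fraction | the 2 Gy rule (2.5 / 2.0 = 1.25, so +25%) |
| 50 Gy and 2 Gy | 50 / 2 | 25 fractions | the count of 20 |
| 2 Gy and 20 fractions | 2 × 20 | 40 Gy | the 50 Gy total (10 / 50 = 20% short) |

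The third row is simply the 40 Gy option, so only the first two deliver 50 Gy.

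**Step 3. Duration.** Assuming 5 fractions per week (not stated), 20 / 5 = 4 weeks and 25 / 5 = 5 weeks. The longer course would run a week past the 4-week intrathecal schedule.

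**Step 4. Biological dose, as an illustration.** Assume the linear-quadratic model with alpha/beta of 2 to 3 Gy; neither is in the documents. The equivalent dose in 2-Gy fractions is EQD2 = D × (d + α/β) / (2 + α/β), where D is total dose and d is dose per fraction.

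- 20 × 2.5 Gy, α/β = 2: 50 × 4.5 / 4 = 56.25 Gy.
- 20 × 2.5 Gy, α/β = 3: 50 × 5.5 / 5 = 55.0 Gy.
- 25 × 2 Gy, either value: 50.0 Gy.

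The two ways of giving 50 Gy therefore differ by 5.0 to 6.25 Gy, or 10% to 12.5%.

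**Step 5. Look for a resolving statement.** The documents give no boost, second daily fraction, exception to 2 Gy, 2.5 Gy fraction or 25-fraction course.

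**The case against.** The best reply is that a specific prescription governs a general introductory sentence. The lower-spine clause gives total dose and fraction count together, which fixes 2.5 Gy, and a 25-fraction course appears nowhere. On that reading the only defect is a missing exception clause. This has force, and 2.5 Gy × 20 is the likelier intent. It is still an inference. Every stated fraction count is 20, but every stated fraction size is 2 Gy. The 4-week drug schedule supports 20 fractions only if 5 are given per week. A spinal fraction size should not have to be worked out by overriding an explicit sentence.

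It can also be said that the consequence is limited, and this stands. Only patients given 50 Gy are affected, and their number is not stated. The wording is identical in both arms, and the primary endpoint and its analysis are untouched. The difficulty with toxicity largely disappears if delivered fractionation is reported.

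Finally, the legend may show only the base regimen. That is fair: its silence on 50 Gy is not a second contradiction. It does mean that the legend cannot settle the first.

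**Conclusion.** The concern holds and should be fixed. The 50 Gy lower-spine option is wrong as written: it implies 2.5 Gy per fraction (+25%) or 25 fractions (+5), and the documents do not say which. That conclusion rests on the protocol's own numbers alone. The 4-versus-5-week difference assumes 5 fractions per week, and the 10% to 12.5% difference in equivalent dose assumes the linear-quadratic model with alpha/beta of 2 to 3 Gy. All 40 Gy prescriptions are consistent. What is at stake is safe delivery and interpretable toxicity in the 50 Gy patients.

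Two gaps in the same sentence are under-specification and add nothing to the weight of this point. No rule says when 50 Gy is used in place of 40 Gy. The first lumbar vertebra is placed in both spinal bands, which matters only when 50 Gy is chosen, since both bands allow 40 Gy.

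**What to change.** If 2.5 Gy × 20 = 50 Gy is intended, state it in the Design section as an explicit exception to the 2 Gy rule for the lower spine. Otherwise write 2 Gy × 25 = 50 Gy. Align the Figure 2 legend with the choice. In the same edit, say when 50 Gy applies and assign the first lumbar vertebra to one band.

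In the report, tabulate delivered lower-spine dose and fractionation by arm beside the toxicity results. This is useful even if treatment is already complete.

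The cost is rewording one sentence and one legend, plus one table. Delivered dose and fraction number must be recorded for each patient if they are not already; the documents do not say whether they are.

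### The SAP applies chi-square and Fisher exact tests to overall survival by patient feature, although OS is a censored time and no binary version of it is defined

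*Combined protocol and SAP*

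**What the plan says.** The Design section makes clinical response rate (CRR) the primary endpoint and puts OS, with safety, among the secondary ones. The Methods section defines the survival variable: "Survival time was measured from the enrollment of the study until death or the last follow-up". It sets no fixed horizon.

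The Statistical Analysis Plan then gives three sentences on survival that suit such a variable: "Survival analysis was performed using the Kaplan-Meier method"; "Log-Rank test was used to compare the survival time of patients"; and "Univariate and multivariate Cox regression analysis were carried out to determine the risk factors of OS". The next sentence adds a fourth approach: "Chi square test and Fisher exact test were used to evaluate the difference of clinical response rate and OS between patients with various features". One significance threshold, P below 0.05, covers everything.

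The readable text contains no OS rate, no landmark time, no dichotomised OS and no rule for patients censored before a landmark. The figure legend expands the abbreviation OS and adds nothing. The figures themselves could not be read.

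**The concern.** Chi-square and Fisher exact tests compare proportions. CRR is a proportion, so they suit it. OS as defined is a time, and for some patients it is known only to exceed a certain value. The sentence therefore cannot be carried out on OS without a choice that the plan does not state.

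The choice nearest to hand is dead or alive at last follow-up. That treats a patient alive after one month like a patient alive after two years. Two consequences follow:

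- Information on timing is discarded, so real prognostic features are missed more often.
- If one feature group has been watched longer than another, it will show more deaths for that reason alone.

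The SAP also directs Cox regression at the same question, which features relate to OS, and does not say how a conflict between the two results would be read.

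**Working it through.** **Inputs.** From the plan: the definition of survival time, the tests named and the 0.05 level. The plan gives no sample size, accrual period, follow-up length or expected survival, so there is no stated figure to reproduce. The following are assumptions: exponential OS with median 4, 6 or 10 months; uniform accrual over 18 months; 30 or 50 patients per feature group; 0–12 months' follow-up after accrual; two-sided tests. The 2×2 test is chi-square on dead/alive at last follow-up, with Fisher if any expected count is below 5.

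**Step 1: proportion dead.** With λ = ln 2 / median and follow-up uniform between a and b months, P(dead) = 1 − [exp(−λa) − exp(−λb)] / [λ(b − a)].

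**Step 2: power at hazard ratio 0.5, equal follow-up, 30 per group.** The second group has twice the median. For the 2×2 test, power ≈ Φ(z − 1.96), with z = difference in proportions dead / √(2p(1 − p)/30) and p the mean proportion. For log-rank, power ≈ Φ(0.693 × √(D/4) − 1.96), with D = 60p expected deaths.

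| Median, follow-up after accrual | Proportions dead | D | 2×2: formula / simulated | Log-rank: formula / simulated |
|---|---|---|---|---|
| 6, 6 months | 0.790, 0.560 | 40.5 | 47% / 48% | 60% / 60% |
| 10, 3 months | 0.536, 0.329 | 26.0 | 36% / 38% | 42% / 42% |
| 4, 12 months | 0.962, 0.821 | 53.5 | 42% / 24% | 72% / 71% |

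In the last row the expected number of survivors per group is 30 × (1 − 0.891) = 3.3, so Fisher applies. Its conservatism accounts for roughly the drop from 42% to 24%. The rest of the gap, about 30 points, is lost timing information. Over all 24 simulated settings the 2×2 test is behind by 3 to 48 points, median 11.

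**Step 3: type I error, equal follow-up.** Simulated 2×2 rejection at hazard ratio 1 is 0–7%; log-rank 4–6%. There is no material inflation.

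**Step 4: type I error, unequal entry dates.** Take median 4 (λ = 0.1733), zero follow-up after accrual and 50 per group. Patients entering in the first 9 months are followed for 9–18 months: P(dead) = 0.894. Those entering later are followed for 0–9 months: P(dead) = 0.494. If 70% of one group and 30% of the other enter early:

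- group 1: 0.7 × 0.894 + 0.3 × 0.494 = 0.774
- group 2: 0.3 × 0.894 + 0.7 × 0.494 = 0.614
- z = 0.160 / √(2 × 0.694 × 0.306 / 50) = 0.160 / 0.0922 = 1.735
- rejection ≈ Φ(1.735 − 1.96) ≈ 41%, with identical true survival.

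The simulated maximum is 42%. With 0–6 months' follow-up the simulated range is 4–42% at 70/30 and 2–13% at 60/40. At about 89% dead and 70/30 it is 3–4% with 30 per group and 9–14% with 50. At 96% dead, where end-of-study censoring is the only kind, it falls to about 1% or less.

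**Step 5: type I error, unequal loss.** Equal entry, 5% versus 15% loss, 3–12 months' follow-up: 2×2 test 5–26%.

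Log-rank stays at 4–6% in Steps 4 and 5. A Kaplan-Meier comparison at 6 months with Greenwood standard errors, run at hazard ratio 1 under equal follow-up, 70/30 entry and 5% versus 15% loss, gives 5–7%.

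**The case against.** The best reply is that the same paragraph already contains the right tools. Kaplan-Meier, log-rank and Cox are planned, and the Cox sentence is the one written expressly for OS risk factors. A reader who relies on those results loses nothing. This stands, and it limits the point to one superfluous, undefined test.

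Second, the authors may have meant survival at a fixed time. If every patient were observed to that time, a chi-square test would be valid and the fault would be only a missing definition. This also stands as a possibility, but no readable text states such a time, so the sentence needs changing on either reading.

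Third, false positives need feature groups with different follow-up, and nothing in the documents predicts that. The 42% needs a 70/30 imbalance, no follow-up after accrual and 50 per group. The 26% likewise comes from one corner (median 4, 12 months, 50 per group); in a separate re-run the other 3–12 month settings gave 5–16%. These are upper ends, not expectations.

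A reader might infer more than this. One inference is that the treatment comparison of OS is compromised. The sentence concerns patient features and does not name the arms; the log-rank sentence naturally covers them, although the SAP does not spell out its groups. Another is that frequent disagreement between the tests is a further harm. At hazard ratio 0.5, equal entry and 3–12 months' follow-up, they disagree in 12–49% of simulated trials. Nearly all of those cases are log-rank significant and the 2×2 test not, so this mostly restates the power loss.

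**Conclusion.** The point holds in limited form. That OS is censored, that these tests are assigned to it and that no binary OS is defined all follow directly from the text. The consequences depend on the assumed dead/alive reading and on accrual, survival and group sizes that the plan does not give.

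On that reading the dependable effect is lower power than the planned log-rank test. Inflated false positives are conditional on follow-up differing by feature, and they are absent with equal follow-up. The documents do not support saying that OS lacks a valid analysis, that the arm comparison is wrong, or that type I error is inflated in general. Nor do they support requiring the multivariate Cox model alone to decide which features are prognostic: no Cox model was run in this check, and the SAP gives no covariate list or selection rule.

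The results at risk are secondary and exploratory. CRR is binary and unaffected. The change should be made, but the primary conclusion does not depend on it.

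**What to change.** Delete *and OS* from the chi-square/Fisher sentence, so that those tests cover CRR and other binary outcomes only. Assess OS by feature with the log-rank and Cox methods already in the SAP.

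If a survival proportion is wanted as well, name its time point before the analysis and compare the Kaplan-Meier estimates there, using Greenwood standard errors. That handles patients censored before the time point.

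The deletion costs two words, and the optional landmark analysis costs one sentence. Neither needs new data.

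### No baseline-KPS-adjusted analysis is prespecified for the MTX versus ara-C comparison of clinical response, and for overall survival the role of the planned Cox model is left open

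*Combined protocol and SAP*

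**What the plan says.** **Response.** The Design section makes CRR the primary endpoint. The Statistical Analysis Plan's only sentence on testing it reads: "Chi square test and Fisher exact test were used to evaluate the difference of clinical response rate and OS between patients with various features". No covariate, stratum or model is given, and the two drug groups are not named as the groups compared.

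**Survival.** "Log-Rank test was used to compare the survival time of patients", again with no stratification and no named groups. Univariate and multivariate Cox regression are also planned, to find risk factors for OS. No covariates are listed, so neither arm nor KPS is certain to be in the model.

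**Allocation.** The Design section says "The patients were randomly divided into two groups" and describes no stratification factor.

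**Where KPS enters.**
- Treatment pathway (Design): "Patients with Karnofsky performance status score (KPS) of ≤ 40 and irradiation intolerance were required to receive induction intrathecal chemotherapy". Concomitant therapy follows once the patient has improved neurologically and can tolerate radiotherapy.
- Endpoint (Table 1): the KPS condition for an obvious response is "≥ 70, or elevation of ≥ 30 compared with the baseline level". For a partial response it is 50-70, or a rise of 10-20 from baseline. The KPS and neurological conditions must both be met.

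**The concern.** Baseline KPS has to be known for the change-from-baseline criteria in Table 1, so using it in the analysis needs no new data. It is also tied to the primary endpoint by construction. If it predicts response, leaving it out of the arm comparison treats explainable variation as noise and costs power. With no balancing at randomisation, a chance excess of low-KPS patients in one arm would move the crude CRR difference even if the drugs were equally effective. The unstratified log-rank test has the same exposure. If an adjusted analysis is chosen only after the data are seen, the choice of covariates is itself open to question.

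**Working it through.** **Inputs.** The documents give no sample size, target difference, expected CRR, KPS distribution, hazard ratio or event count, so there is no figure of the plan's own to reproduce. Everything numerical below is assumed: 1:1 unstratified allocation, two-sided 0.05, and the ranges shown. The plan gives the 0.05 threshold but not its sidedness.

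**Step 1: does Table 1 make baseline KPS relevant?** A patient who enters at KPS 50-70 already meets the KPS condition for a partial response, and one who enters at 70 or more already meets it for an obvious response, with no gain in KPS. A patient at 40 or less must gain KPS to meet either. Neurological improvement is still required of everyone. This shows that baseline KPS can matter, but it does not fix the size of the CRR gap between KPS groups.

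**Step 2: chance imbalance.** With share p at KPS of 40 or less and n per arm, the SD of the between-arm difference in that share is √(2p(1−p)/n).
- p = 0.3, n = 50: √(2 × 0.21/50) = 0.092
- p = 0.5, n = 30: √(2 × 0.25/30) = 0.129

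The SD is therefore about 9 to 13 points. If the drugs are equal, the shift in the crude CRR difference is (difference in low-KPS share) × (CRR gap between KPS groups). For a 2-SD imbalance:
- smallest: 2 × 0.092 × 0.30 = 0.055
- largest: 2 × 0.129 × 0.60 = 0.155

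That is about 6 to 15 points for gaps of 30 to 60 points. It shrinks towards zero with the gap, and a 2-SD imbalance is roughly a 1-in-20 event.

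**Step 3: power for CRR, crude chi-square versus Cochran-Mantel-Haenszel (CMH).** Simulation with 40,000 trials per scenario, 30-50 per arm, 30% or 50% with low KPS, within-stratum odds ratio 3:

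| CRR gap between KPS groups (control) | Change in power, crude to CMH |
|---|---|
| none (60/60) | −0.8 to −0.2 points |
| 10 points | −0.4 to +0.4 |
| 20 points (50/70) | +0.1 to +1.4 |
| 30 to 60 points (40/70, 30/80, 20/80) | about +2 to +14 |

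Examples from the last row:
- 41% to 43% (40/70, 30 per arm, 30% low KPS)
- 53% to 62% (30/80, 50 per arm, 50% low KPS)
- 44% to 58% (20/80, 50 per arm, 50% low KPS)

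A second set of assumptions (half with low KPS, overall rates 60% versus 80%, 50 per arm) gives the same picture: 59% to 60%, 60% to 66% and 59% to 73% for gaps of 20, 40 and 60 points.

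**Step 4: type I error.** Without adjustment, the crude test stayed near 5% in all scenarios (4.7% to 5.6%). The problem is conditional. With 50 per arm and half at low KPS, the arms differ by at least 15 points in low-KPS share about 13% of the time. Given that, the crude test rejects a true null about 7%, 11% or 18% of the time for gaps of 20, 40 or 60 points.

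**Step 5: OS.** Unstratified versus KPS-stratified log-rank, assuming an arm hazard ratio of 0.6, half with low KPS, 90% of patients with events and 50 per arm:
- KPS hazard ratio 1.5: 64% to 66%
- KPS hazard ratio 2: 61% to 66%
- KPS hazard ratio 3: 52% to 66%

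Across 30 to 75 per arm the change is −1 to +2, +2 to +5 and +9 to +14 points respectively.

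**The case against.** The strongest reply is that an unadjusted primary test is an acceptable choice in a randomised phase II trial. Randomisation keeps it valid, and the documents do not show that KPS is strongly prognostic for response. Table 1 offers low-KPS patients a route through change from baseline and others a route through absolute cut-offs, so the CRR gap could be small. With a gap of 10 points or less, adjustment changes nothing worth having. This stands, and it is why the lower end of the gain is zero.

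Three stronger readings are tempting, and the documents do not support them.
- *The survival analysis ignores KPS.* A multivariate Cox model is planned and could hold both arm and KPS. The gap is that the plan does not say so, or say whether that model informs the drug comparison.
- *KPS alone decides the treatment pathway.* Induction requires KPS of 40 or less together with irradiation intolerance, and the Figure 2 footnote repeats both conditions. The pathway rule therefore does not by itself justify a cut at 40. The better support is Table 1, where 50 is the lowest absolute KPS cut-off for response.
- *The plan commits to a crude MTX versus ara-C test of CRR.* The sentence on the chi-square and Fisher tests does not name the arms. That the crude test is the primary comparison is an inference, and the missing statement is itself part of the point.

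What survives is that no adjusted analysis of any kind is given for the primary endpoint, although the natural covariate is already to hand.

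**Conclusion.** The point holds as a free improvement in precision and clarity. The plan gives no KPS-adjusted analysis of CRR, does not state the arm comparison of CRR, and leaves the Cox model for OS unspecified.

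A reader might infer that the crude comparison is biased or has an inflated error rate. It does not: its type I error holds on average, and only a particular realised imbalance distorts a particular result.

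A reader might also infer a definite loss of power. The supportable range is about 0 to 14 points for CRR. It rests on assumed arm sizes, low-KPS share, odds ratio and CRR gap, none of which the documents give. The top of the range needs a 60-point CRR gap between KPS groups. The omission is certain; its size is not.

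**What to change.** In the Statistical Analysis Plan:

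1. **CRR.** State that the primary test compares MTX with ara-C by a CMH test stratified by baseline KPS (40 or less versus above 40), or by a logistic model with arm and baseline KPS. Report the adjusted difference or odds ratio with its 95% CI, and give the crude chi-square or Fisher test as support.
2. **OS.** Compare the arms by a log-rank test stratified by the same factor. Add a Cox model that always keeps arm and baseline KPS, whatever other risk factors are explored.

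The cost is a few lines of wording. No new data or patients are needed, and the methods are in standard software. If KPS proves only weakly prognostic, the simulated loss of power for CRR from stratifying is under 1 point.

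### The Figure 2 legend gives intrathecal methotrexate as 10 mg while the protocol text gives 15 mg, so the dose in one of the two randomised arms is contradictory

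*Combined protocol and SAP*

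**What the plan says.** The Design section gives the MTX dose three times, always as 15 mg:

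- Background: "The common regimen of intrathecal dose of MTX and ara-C was 15mg and 50mg, respectively".
- Concomitant regimen: "MTX 15 mg, plus dexamethasone 5 mg, or ara-C 50mg, plus dexamethasone 5 mg, once per week, 4 weeks in total".
- Induction, for patients with KPS of 40 or less who cannot tolerate irradiation: "induction intrathecal chemotherapy (MTX 15 mg, or ara-C 50mg, plus dexamethasone 5 mg, twice per week".

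The same section refers the reader to the figures: "The study plan and regimen schema is provided in" Figures 1 and 2. The legend of Figure 2, printed after the SAP text and the reference, then states "Intrathecal chemotherapy: Methotrexate 10 mg/ Cytarabine 50mg+dexamethasone 5 mg". That line is the legend's only statement of the intrathecal dose. The legend also has a footnote on who receives induction, but gives no separate dose for it.

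Randomisation is between "involved-field radiotherapy (RT) combined with concurrent intrathecal-MTX or intrathecal-ara-C, respectively". The primary endpoint is clinical response rate (CRR); safety and overall survival (OS) are secondary.

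**The concern.** Comparing the two intrathecal drugs is a stated purpose of the trial, and the arms are meant to differ only in that drug. The plan nevertheless gives two values for the dose of one of them, both in current text, and sends staff to the place where the second value stands. A regimen schema is a natural working reference for a ward or pharmacy.

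If some or all MTX patients were dosed from the schema, the MTX arm would be at a lower dose, or a mixture of two doses, while the ara-C arm was uniform. A difference in CRR, OS or adverse events could then arise partly from dose. The SAP has no rule for handling departures from the planned dose, so the analysis would not bring this to light. Separately, an ambiguous dose of an intrathecal cytotoxic is a patient-safety matter in its own right. Measured against the protocol's own 15 mg, following the legend means under-dosing.

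**Working it through.** The plan rests no statistical figure on this dose, so there is nothing of its own to reproduce first. The check is a comparison of every dose statement, followed by simple arithmetic.

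**Step 1. Dose statements side by side**

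| Place | MTX | ara-C | Dexamethasone |
|---|---|---|---|
| Design, common regimen | 15 mg | 50 mg | not stated |
| Design, concomitant (weekly, 4 weeks) | 15 mg | 50 mg | 5 mg |
| Design, induction (twice weekly) | 15 mg | 50 mg | 5 mg |
| Figure 2 legend | **10 mg** | 50 mg | 5 mg |

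Only the MTX entry in the last row differs.

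**Step 2. Can 10 mg be explained from the document?**

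- As the induction dose: no, the text gives induction as "MTX 15 mg, or ara-C 50mg, plus dexamethasone 5 mg, twice per week".
- As a reduced or alternative dose level: no, none is described.
- As superseded text: no, the legend is current and the document contains no amendment that changes the dose.
- As a text-extraction fault: unlikely. The line is complete and its other two doses match the text. The drawing itself is not available, so it cannot be compared with its legend.

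**Step 3. Size per injection**

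- Legend relative to text: 10/15 − 1 = −33.3%, a shortfall of 15 − 10 = 5 mg.
- Text relative to legend: 15/10 − 1 = +50%.

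**Step 4. Size over the concomitant phase (4 weekly injections)**

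- MTX by the text: 4 × 15 = 60 mg.
- MTX by the legend: 4 × 10 = 40 mg, a gap of 20 mg.
- ara-C by either source: 4 × 50 = 200 mg.

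**Step 5. Patients who also have induction**

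The number of induction injections, k, is not given. If all four concomitant injections follow, the gap is 5 × (4 + k) mg. The values of k below are assumptions for illustration.

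| k | Text | Legend | Gap |
|---|---|---|---|
| 0 | 4 × 15 = 60 mg | 4 × 10 = 40 mg | 20 mg |
| 2 (one week) | 6 × 15 = 90 mg | 6 × 10 = 60 mg | 30 mg |
| 4 (two weeks) | 8 × 15 = 120 mg | 8 × 10 = 80 mg | 40 mg |

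The relative shortfall stays at 33% throughout; only the absolute gap grows.

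**Step 6. Effect on the arm**

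If a fraction p of MTX injections followed the legend, the mean MTX dose per injection would be 15 − 5p mg. This runs from 15 mg (p = 0) to 10 mg (p = 1). The document gives no information on p.

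**The case against.** The strongest reply is that the intended dose can be recovered. Both operative statements and the background sentence say 15 mg, and one figure legend disagrees. The legend is loose elsewhere too: it gives a flat 40 Gy for radiotherapy, although the text allows 50 Gy at the first lumbar vertebra and below. A slip in the legend is therefore the likeliest explanation. Further, nothing shows that anyone received 10 mg or that the figure was used for prescribing. Only one hospital's ethics committee is named, so there is no sign of scattered sites working from different pages. The error would lie on the side of under-dosing. The induction gap has no known size. Much of the document is in the past tense, so treatment may be over and a notice to staff may reach nobody. On this view it is an editorial inconsistency and not a decision about design.

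Much of this stands. The legend is probably the error, mixing of doses is not shown, and no statistical figure in the plan changes. What remains is that no clause gives the text precedence and the text itself directs readers to the figures. The dose of a randomised drug is part of the definition of the intervention. Only treatment records can show what was given, so inference from the wording does not settle it. If treatment has ended, the correction and the record check are still needed.

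**Conclusion.** The concern holds and must be fixed. The plan gives two MTX doses, 15 mg and 10 mg, and nothing in the document reconciles them. The discrepancy is 33% per injection (40 mg against 60 mg over the concomitant phase) and falls on one randomised arm only.

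The existence and size of the conflict follow directly from the text and need no assumption beyond completion of the four planned injections. The threat to the comparison is conditional: it arises only if some or all injections followed the legend, and the document neither shows nor excludes this. That 15 mg was intended is a reasonable inference from three statements against one, but the plan does not state which source governs.

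**What to change.** 1. State one MTX dose everywhere. Unless records show otherwise, change the Figure 2 legend from 10 mg to 15 mg. All four dose statements then agree, and the planned concomitant total is 60 mg. If patients are still being treated, tell the treating staff and pharmacy.
2. Check the treatment records for the MTX dose actually given, in the induction and concomitant phases, and state it in the report.
3. If both doses were used, keep the as-randomised comparison primary. In addition, report CRR, OS and adverse events within the MTX arm by dose given, as description only, because dose would not have been randomised.

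The cost is a one-line correction and a review of existing records. No patients, visits or procedures are added.
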